6.0 STUDY PROCEDURES

6.1 Screening/Baseline Procedures

Assessments performed exclusively to determine eligibility for this study will be done only after obtaining informed consent. Assessments performed for clinical

indications (not exclusively to determine study eligibility) may be used for baseline values even if the studies were done before informed consent was obtained.

6.2 Time and Events Table/Schedule of Events/Study Calendar

Table 5. Study Calendar							
Procedures	Screening ¹	Cycle 1		Cycle X		EOT Visit ⁸	Follow-Up Q3 months +/- 1 week ⁹
		Day 1	Day 15	Day 1	Day 15		
Informed Consent	X						
History, Physical Examination	X	X		X		X	
Weight, BSA	X	X		X		X	
Vital Signs	X	X	X	X		X	
Performance Status	X	X		X		X	
Toxicity Evaluations		X	X	X			
Scans with Tumor Measurements	X			X ⁵			
CBC with differential	X	X	X	X			
CMP ²	X	X	X	X			
AFP		X		X ¹⁰		X	
PT/INR, PTT	X						
Pregnancy Test ³	X						
UPCR ¹¹		X		X			
TSH, Free T4 and T3		X		X			
Concomitant Medication Review	X	X		X			
12 lead ECG	X						
PK Blood ¹²			X	X ¹²	X ¹²		
Research Blood ⁴		X		X		X	
Tissue ⁶	X						X
Study Drug Administration ⁷		X	X	X			
Survival Follow-up							X

1. All screening procedures to be completed within 2 weeks of enrollment, except imaging which should be ≤ 4 weeks. Protocol treatment is to begin ≤14 days of enrollment.

-
2. Comprehensive metabolic panel includes BUN/creatinine, sodium, potassium, chloride, glucose, calcium, alkaline phosphatase, AST, ALT, total bilirubin and total protein.
 3. Required for females of childbearing potential. Serum or urine pregnancy test per site investigator discretion.
 4. Cycle 1 Day 1 specimens will be collected prior to administration of initial dose, and Cycle X Day 1 specimens will be collected on Cycle 4 Day 1. Refer to the lab manual for sample collection and processing details.
 5. MRI or CT (abdomen/pelvis) with contrast along with CT chest with/without contrast will be assessed every 8 ± 1 weeks starting from C1D1. Imaging assessment of scans at the site should be completed by either a radiologist or an imaging core, and not by the oncologist nor via abstraction of data from the subjective/clinical radiology report.
 6. Pre-treatment, diagnostic pathology specimens obtained in the course of standard biopsy or surgery, if available. Procurement of tissue is mandatory for enrollment, if available. If tissue from initial biopsy is not available, a repeat biopsy is NOT required and patient will be eligible for enrollment. Post-treatment tissue collection, if available. Refer to the lab manual for sample collection and processing details.
 7. See Section 5.1 for details. Study drug administration with associated labs will have a window of ± 3 days.
 8. End of treatment (EOT) visit should be completed within 30 days of last treatment.
 9. Patients will be followed every 3 months via telephone or office visit documentation for up to 2 years from treatment discontinuation or until death, whichever comes first, or 3 years after first date of treatment initiation for those that remain on treatment.
 10. Check AFP every 8 +/- 1 weeks. May be delayed if drug is not administered within the window.
 11. Urine protein/creatinine ratio
 12. Pharmacokinetic blood draws (pre-dose) prior to Cycle 1 Day 15, Cycle 2 Day 1, Cycle 2 Day 15 and Cycle 3 Day 1. See lab manual for details.

7.0 MEASUREMENT OF EFFECT

7.1 Antitumor Effect- Solid Tumors

Objective response assessment will be determined by review of CT or MR scans of the chest, abdomen and pelvis using RECIST v1.1 every 8 weeks +/- 1 week while patients are on treatment (Eisenhauer, Therasse et al. 2009) .

7.1.1 Definitions

Evaluable for toxicity. All patients will be evaluable for toxicity from the time of their first treatment with study drug.

Evaluable for primary endpoint, DLT/MTD assessment. All patients that receive at least one dose of study therapy will be considered evaluable. Patients enrolled to therapy but that never receive study therapy will be replaced.

Evaluable for objective response. All enrolled patients who received at least 1 cycle(s) of therapy, and had their disease re-evaluated will be considered evaluable for response. These patients will have their response classified according to the definitions stated below. (Note: Patients who exhibit objective disease progression prior to the end of cycle 1 will also be considered evaluable.)

7.1.2 Disease Parameters

Measurable disease. Measurable lesions are defined as those that can be accurately measured in at least one dimension (longest diameter in the plane of measurement is to be recorded) with a minimum size of:

- 10 mm by CT scan (irrespective of scanner type) for studies with a slice thickness of ≤ 5 mm or twice the slice thickness or MRI
- 10 mm caliper measurement by clinical exam (lesions which cannot be accurately measured with calipers should be recorded as non-measurable)
- 20 mm by chest X-ray (if clearly defined and surrounded by aerated lung)

All tumor measurements must be recorded in millimeters (or decimal fractions of centimeters).

Malignant lymph nodes: To be considered pathologically enlarged and measurable, a lymph node must be ≥ 15 mm in short axis when assessed by CT scan (CT scan slice thickness recommended to be no greater than 5 mm). At baseline and in follow-up, only the short axis will be measured and followed.

Note: Tumor lesions that are situated in a previously irradiated area will only be considered measurable, if they have had subsequent progression by at least 5 mm.

Non-measurable disease. All other lesions (or sites of disease), including small lesions (longest diameter < 10 mm using CT scan), are considered non-measurable disease. Bone lesions without measurable soft tissue component, leptomeningeal disease, ascites, pleural/pericardial effusions, lymphangitis cutis/pulmonitis, inflammatory breast disease, abdominal masses (not followed by CT or MRI), and cystic lesions are all non-measurable.

Target lesions. All measurable lesions up to a maximum of 2 lesions per organ and 5 lesions in total should be identified as target lesions and recorded and

measured at baseline. Target lesions should be selected on the basis of their size (non-nodal lesions with the longest diameter), be representative of all involved organ(s), but in addition should be those that lend themselves to reproducible repeated measurements.

Lymph nodes merit special mention since they are normal anatomical structures that may be visible by imaging even if not involved by tumor. Pathological nodes that are defined as measurable and may be identified as target lesions must meet the criterion of a short axis of ≥ 15 mm by CT scan. Only the short axis of these nodes will contribute to the baseline sum. The short axis of the node is the diameter normally used by radiologists to judge if a node is involved by solid tumor. Nodal size is normally reported as two dimensions in the plane in which the image is obtained (for CT scan this is almost always the axial plane; for MRI the plane of acquisition may be axial, sagittal or coronal). The smaller of these measures is the short axis. For example, an abdominal node which is reported as being 20 mm x 30 mm has a short axis of 20 mm and qualifies as a malignant, measurable node. In this example, 20 mm should be recorded as the nodal measurement. All other pathological nodes (those with short axis ≥ 10 mm but < 15 mm) should be considered non-target lesions. Nodes that have a short axis < 10 mm are considered non-pathological and should not be recorded or followed. A sum of the diameters (longest for non-nodal lesions, short axis for nodal lesions) for all target lesions will be calculated and reported as the baseline sum of diameters. If lymph nodes are to be included in the sum, then as noted above, only the short axis is added into the sum. The baseline sum of diameters will be used as reference to further characterize any objective tumor regression in the measurable dimension of the disease.

Non-target lesions. All other lesions (or sites of disease) including pathological lymph nodes should be identified as non-target lesions and should also be recorded at baseline. Measurements are not required, and these lesions should be followed as 'present', 'absent', or in **rare** cases 'unequivocal progression' (more details to follow). In addition, it is possible to record multiple non-target lesions involving the same organ as a single item on the case record form (e.g. 'multiple enlarged pelvic lymph nodes' or 'multiple liver metastases').

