3.1 Eligibility Criteria

- 3.1.1 Patients must have a radiologically consistent (early enhancement and delayed enhancement washout) or pathologically confirmed diagnosis of hepatocellular carcinoma that is not eligible for curative resection, transplantation, or ablative therapies.
- 3.1.2 Prior radiation, liver directed therapy (including bland, chemo- or radio-embolization, or ablation), or hepatic resection are permitted if ≥ 4 weeks from start of therapy. Extra-hepatic palliative radiation is permitted if completed ≥ 2 weeks prior to first dose of study therapy and the patient has recovered to \leq grade 1 toxicity.
- 3.1.3 Patients must have radiographically measurable disease (RECIST1.1) in at least one site not previously treated or with progression after radiation or liver directed therapy (including bland, chemo- or radio-embolization, or ablation) either within the liver or in a metastatic site.
- 3.1.4 Patients must have either progressed or deemed intolerant of first-line systemic therapy. More than one line of systemic therapy is not permitted. The last dose should be at least 2 weeks from first dose of study therapy. Prior treatment may not contain cabozantinib.
- 3.1.5 Recovery to \leq grade 1 from toxicities related to any prior treatments, unless the AEs were clinically non-significant and/or stable on supportive therapy
- 3.1.6 Must be ≥ 18 years of age.
- 3.1.7 Must have a Child-Pugh score of B7 or B8
- 3.1.8 Must have an ECOG performance status of 0-1.
- 3.1.9 Ability to understand and willingness to sign IRB-approved informed consent.
- 3.1.10 Willing to provide archived tissue, if available, from a previous diagnostic biopsy.
- 3.1.11 Must be able to tolerate CT and/or MRI with contrast.
- 3.1.12 Adequate organ function obtained ≤ 2 weeks prior to enrollment:

absolute neutrophil count	$\geq 1200/\text{mm}^3$
hemoglobin	$\geq 8.5 \text{ g/dL}$
platelets	$\geq 60,000/\text{mm}^3$
serum creatinine	$\leq 1.5 \times \text{ULN}$
creatinine clearance	$\geq 40 \text{ mL/min}$
albumin	$\geq 2.8 \text{ g/dL}$
AST/ALT	$\leq 5.0 \times \text{ULN}$
total bilirubin	$\leq 3.0 \text{ mg/dL}$
INR	≤ 2.3

-
- 3.1.13 Must not have uncontrolled ascites (requiring paracentesis within 3 months of screening) or hepatic encephalopathy requiring hospitalization (within 6 months of screening)
- 3.1.14 Must not have prior history of organ transplantation.

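### Section 7.1.2 lets embolised or ablated lesions that have not progressed serve as target lesions, which can distort ORR in either direction and delay progression called on target growth

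*Combined protocol and SAP*

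**What the plan says.** Criterion 3.1.2 admits patients with earlier local treatment: "Prior radiation, liver directed therapy (including bland, chemo- or radio-embolization, or ablation), or hepatic resection are permitted", subject to an interval of at least 4 weeks before therapy starts. Criterion 3.1.3 then asks for "radiographically measurable disease (RECIST1.1) in at least one site not previously treated or with progression after radiation or liver directed therapy", and lists bland, chemo- and radio-embolization and ablation as liver-directed therapy.

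Which lesions are measured is decided in Section 7.1.2. Its size limit for CT (slices up to 5 mm) or MRI is 10 mm. Its only limit based on prior treatment concerns lesions "situated in a previously irradiated area will only be considered measurable, if they have had subsequent progression by at least 5 mm". On selection it says "All measurable lesions up to a maximum of 2 lesions per organ and 5 lesions in total should be identified as target lesions" and "Target lesions should be selected on the basis of their size". It adds that targets should represent all involved organs and "should be those that lend themselves to reproducible repeated measurements". Everything else is non-target and need not be measured.

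Section 7.1.4.1 sets PR at a 30% fall in the target sum from baseline. Target PD is a 20% rise from the smallest sum, with at least 5 mm absolute increase. Section 11.4 reports ORR with an exact 95% interval and PFS by Kaplan-Meier. TTP is a secondary objective in Section 2.2.

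**The concern.** The two sections apply different standards to a treated lesion. Criterion 3.1.3 recognises that a lesion treated by embolization or ablation is poor evidence of active disease unless it has since progressed, but it works at patient level: one qualifying site is enough. Section 7.1.2 works at lesion level and carries the standard over only for irradiated areas.

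A site that follows 7.1.2 as written can therefore put a large treated lesion into the target sum because of its size. If the liver holds two such lesions, both larger than the liver lesion that made the patient eligible, the cap of two per organ can leave the qualifying lesion unmeasured. The target sum would then partly, or entirely, track tissue whose size reflects an earlier procedure and not cabozantinib. ORR and the target-growth component of PFS and TTP depend on that sum.

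**Working it through.** The documents state no figure that depends on this rule, so there is none to reproduce. The 32 patients in Section 11.2 serve the dose-toxicity estimate. What follows is algebra on the thresholds in Section 7.1.4.1; lesion sizes, shares and growth rates are assumptions.

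**1. Treated lesion inert.** Let w be its share of the baseline target sum S. Active tumour contributes (1-w)S. PR needs a fall of 0.30S, all of it from active tumour, so the required shrinkage is 0.30/(1-w). If the sum has not fallen below baseline, target PD needs a rise of 0.20S, so the required growth is 0.20/(1-w).

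| w (assumed) | Active shrinkage for PR | Active growth for target PD |
|---|---|---|
| 0 | 30% | 20% |
| 0.25 | 40% | 27% |
| 0.50 | 60% | 40% |
| 0.60 | 75% | 50% |
| 0.70 | 100% | 67% |

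Above w = 0.70, PR cannot be reached by shrinkage of active tumour alone. At w = 1 (both liver targets treated and inert, liver-only disease) the target sum registers neither response nor growth.

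**2. Example: 50 mm treated and inert plus 30 mm active (S = 80 mm).**
- As written: PR needs 0.30 × 80 = 24 mm, which is 24/30 = 80% of the active lesion. PD needs 0.20 × 80 = 16 mm, or 16/30 = 53%.
- Treated lesion excluded: PR needs 9 mm (30%) and PD needs 6 mm (20%).

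**3. PD after shrinkage.** PD is counted from the smallest sum. Take 60 mm inert plus 40 mm active, where the active lesion falls to 20 mm. The smallest sum is 80 mm, so PD needs 16 mm of regrowth on 20 mm, or 80%. The baseline formula would give 0.20/0.40 = 50%, so it understates the requirement once the sum has fallen.

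**4. Treated lesion still involuting.** In the 50 + 30 mm example, if the treated lesion shrinks by a fraction s, the active lesion must shrink by (24 - 50s)/30 for PR. At s = 0.10, 0.20 and 0.30 this is 63%, 47% and 30%. At s = 24/50 = 0.48, PR is recorded with no change in active tumour. The ORR error can therefore run either way.

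**5. Timing of target PD.** Assume exponential growth with volume doubling time D, the treated lesion inert and the sum never below baseline. Time to PD is 3D × log2(1 + required growth). For the 50 + 30 mm example:

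| D (weeks) | Active lesion alone | With treated lesion |
|---|---|---|
| 8 | 6.3 weeks | 14.8 weeks |
| 16 | 12.6 weeks | 29.6 weeks |
| 24 | 18.9 weeks | 44.4 weeks |

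On the 8-week scan schedule, target PD is first seen at week 16, 32 or 48 instead of week 8, 16 or 24.

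**6. Scale for ORR.** One reclassified patient moves ORR by 1/32 = 3.1 points. For example, 4/32 = 12.5% (exact 95% CI 3.5 to 29.0%) becomes 3/32 = 9.4% (2.0 to 25.0%).

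**The case against.** The strongest reply is that this is a gap in wording with limited reach. Much of that stands.

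- *Size is not the only selection criterion.* Targets must also be representative and reproducibly measurable, cystic lesions are non-measurable, and Table 5 (footnote 5) requires reading by a radiologist or an imaging core. So a treated lesion can be selected; it need not be. But none of these qualifiers mentions prior treatment or viability, and Section 10.4 collects CT scans only for banking and exploratory work, so no central read is described that would harmonise target choice.
- *Other routes to progression.* New lesions, unequivocal non-target progression and clinical progression all count. The delay therefore applies only to PD called on target growth. The non-target route is a weak backstop, since Sections 7.1.2 and 7.1.4.3 describe it as rare or exceptional. A missed PR has no alternative route.
- *Radio-embolised lesions* may already count as lying in an irradiated area. The gap is clearest for bland or chemo-embolization and ablation.
- *RECIST v1.1 is the cited standard* (Sections 7.1 and 11.4). Whether it fills the gap cannot be settled from the documents; the protocol writes out its own note, and sites will apply that.

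A reader might infer that ORR is biased downward, PFS and TTP upward, and that patients will be treated past progression. The documents do not support this. The direction for ORR requires the treated lesion to be inert, and 3.1.2 permits local therapy as recently as 4 weeks before the start, so involution may be continuing. Section 5.5 also lets treatment end for reasons other than progression under Section 7.

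**Conclusion.** The mismatch between 7.1.2 and 3.1.3 is real and follows from the text alone. It can distort ORR in either direction and can delay progression called on target growth. For an individual patient the effect can be large: with half the baseline sum inert, the active-tumour thresholds double to 60% and 40%.

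At trial level the size is unknown. The documents do not say how many patients have treated lesions without progression, or what share of the target sum these would form. Displacement of the qualifying lesion also needs a particular configuration, such as two larger treated lesions in the same organ. Only ORR, PFS and TTP are affected. The primary DLT endpoint, the dose selection and the 32 patients are not, and no hypothesis test or decision rule rests on the affected endpoints. It is worth correcting because the correction is cheap, not because it threatens the trial's main conclusion.

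**What to change.** Keep the existing 5 mm note for irradiated areas and add to Section 7.1.2:

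> Lesions previously treated by embolization (bland, chemo- or radio-) or ablation are measurable and may be target lesions only if they have shown progression since that treatment, as in 3.1.3; otherwise record them as non-target. At least one lesion satisfying 3.1.3 must be a target lesion.

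Do not extend the 5 mm minimum to embolised or ablated lesions. Criterion 3.1.3 asks for progression and states no size, so a patient whose only qualifying lesion had progressed by less than 5 mm would be eligible but have no target. The same tension already exists for irradiated lesions, so the 5 mm rule in 7.1.2 and the wording of 3.1.3 should be reconciled in the same amendment. Otherwise the new requirement for a qualifying target could not always be met. The text should also say whether a radio-embolised lesion falls under the irradiation note, the new sentence, or both.

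The cost is two sentences, the reconciliation and a matching instruction to readers. Some patients will have fewer target lesions. Sample size and dose-finding do not change.

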7.1.3 Guidelines for Evaluation of Measurable Disease

All measurements should be recorded in metric notation, using calipers if clinically assessed. All baseline evaluations should be performed as close as possible to the treatment start date and never more than 4 weeks before the beginning of the treatment.

The same method of assessment and the same technique should be used to characterize each identified and reported lesion at baseline and during subsequent follow-up studies. Imaging-based evaluation should always be done rather than clinical examination unless the lesion(s) being followed cannot be imaged but are assessable by clinical exam.

Clinical lesions: Clinical lesions will only be considered measurable when they are superficial and > 10 mm diameter as assessed using calipers (e.g. skin nodules). For the case of skin lesions, documentation by color photography including a ruler to estimate the size of the lesion is suggested. As noted above, when lesions can be evaluated by both clinical exam and imaging, imaging evaluation should be undertaken since it is more objective and may also be reviewed at the end of the study.

CT, MRI: MR is the best currently available and reproducible method to measure lesions selected for response assessment in HCC. If CT is completed, the guideline has defined measurability of lesions on CT scan based on the assumption that CT slice thickness is 5mm or less. When CT scans have slice thickness greater than 5 mm, the minimum size for a measurable lesion should be twice the slice thickness.

Ultrasound: Ultrasound is not useful in assessment of lesion size and should not be used as a method of measurement. Ultrasound examinations cannot be reproduced in their entirety for independent review at a later date and, because they are operator dependent, it cannot be guaranteed that the same technique and measurements will be taken from one assessment to the next. If new lesions are identified by ultrasound in the course of the study, confirmation by CT or MRI is advised.

Endoscopy, laparoscopy: The utilization of these techniques for objective tumor evaluation is not advised. However, they can be useful to confirm complete pathological response when biopsies are obtained or to determine relapse in trials where recurrence following complete response or surgical resection is an endpoint.

Tumor markers: Tumor markers alone cannot be used to assess objective tumor response.

7.1.4 Response Criteria

7.1.4.1 Evaluation of Target Lesions

Complete Response (CR): Disappearance of all target lesions, determined by two separate observations conducted not less than 4 weeks apart. There can be no appearance of new lesions.

Partial Response (PR): At least a 30% decrease in the sum of the longest diameter (LD) of target lesions, taking as reference the baseline sum LD. There can be no appearance of new lesions.

Progressive Disease (PD): At least a 20% increase in the sum of the LD of target lesions (with a minimum absolute increase of 5 mm), taking as reference the smallest sum LD recorded since the treatment started, or the appearance of one or more new lesions.

Stable Disease (SD): Neither sufficient shrinkage to qualify for PR (taking as reference the baseline sum LD) nor sufficient increase to qualify for PD (taking as reference the smallest sum LD since the treatment started).

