7.1.4.3 Evaluation of Best Overall Response

The best overall response is the best response recorded from the start of the treatment until disease progression/recurrence (taking as reference for progressive disease the smallest measurements recorded since the treatment started). The patient's best response assignment will depend on the achievement of both measurement and confirmation criteria.

Table 6. Response Evaluation as per RECISTv1.1				
Target Lesions	Non-Target Lesions	New Lesions	Overall Response per RECISTv1.1	Confirmed Response for this Category Requires:
CR	CR	No	CR	>4 wks. confirmation
CR	CR Non-CR/PD	No	PR	≥4 wks. confirmation
PR	CR Non-CR/PD	No		
SD	CR Non-CR/PD	No	SD	Documented at least once ≥4 wks. from baseline
PD	Any	Any	PD	
Any	PD*	Any		
Any	Any	Yes		

* Only in exceptional circumstances, unequivocal progression in non-target lesions may be accepted as disease progression.
 
Note: Patients with a global deterioration of health status requiring discontinuation of treatment without objective evidence of disease progression at that time should be reported as “symptomatic deterioration”. Every effort should be made to document the objective progression even after discontinuation of treatment.
				

NA=not applicable

Note: If subjects respond to treatment and are able to have their disease resected, the patient's response will be assessed prior to the surgery.

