7.1.5 Duration of Response

Duration of overall response: The duration of overall response is measured from the time measurement criteria are met for CR or PR (whichever is first recorded) until the first date that recurrent or progressive disease is objectively documented (taking as reference for progressive disease the smallest measurements recorded since the treatment started).

Duration of stable disease: Stable disease is measured from the start of the treatment until the criteria for progression are met, taking as reference the smallest measurements recorded since the treatment started.

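### As written, the progression reference leaves out the pre-treatment baseline sum, so progression by target-lesion growth alone can be dated one or more scans late

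*Combined protocol and SAP*

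**What the plan says.** Section 7.1.4.1 defines progressive disease (PD) in target lesions as "At least a 20% increase in the sum of the LD of target lesions (with a minimum absolute increase of 5 mm"), with the reference given as "taking as reference the smallest sum LD recorded since the treatment started, or the appearance of one or more new lesions". Stable disease (SD) in the same section uses two references: the baseline sum for shrinkage, and for growth "nor sufficient increase to qualify for PD (taking as reference the smallest sum LD since the treatment started").

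The same reference appears in Section 7.1.4.3, "taking as reference for progressive disease the smallest measurements recorded since the treatment started", and twice in Section 7.1.5, once for how long a response lasts and once for how long SD lasts ("Stable disease is measured from the start of the treatment until the criteria for progression are met, taking as reference the smallest measurements recorded since"). That makes five places.

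The baseline sum has a separate role. Section 7.1.2 says "The baseline sum of diameters will be used as reference to further characterize any objective tumor regression in the measurable dimension of the disease" and does not mention growth. Section 7.1.3 fixes its timing: "All baseline evaluations should be performed as close as possible to the treatment start date and never more than 4 weeks before" treatment begins. The study calendar (Section 6.2) puts the baseline scan at screening and later scans every 8 ± 1 weeks from cycle 1 day 1.

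Sections 7.1 and 11.4 and Table 6 name RECIST v1.1 as the response standard. Section 5.5 ends treatment on progression as Section 7.0 defines it.

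**The concern.** A pre-treatment sum is not among the sums recorded after treatment started. Taken at its word, the rule compares the first on-treatment scan with itself, so target-lesion growth since baseline cannot count there. Growth between baseline and that scan is not recovered later either, because the larger first on-treatment sum becomes the starting reference.

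The wording is hard to dismiss as shorthand. The SD definition sets the baseline sum and the smallest sum since treatment started side by side as two different references, and Section 7.1.2 ties baseline to regression.

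At stake are the PD date used for PFS and TTP (Section 2.4.2) and the classification of patients as SD or PD. Both endpoints are secondary objectives of a single-arm trial, so no concurrent control group would share the error and cancel it. The error can only move PD later.

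**Working it through.** The plan states no target, threshold or event count for PFS or TTP, so there is no figure to reproduce. The check applies the written rule to example sums and then asks how far a summary could move.

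**Step 1: the two rules.** Let B be the baseline sum, s the current sum and m the smallest on-treatment sum up to and including the current scan. PD by target growth requires s ≥ 1.2 × R and s − R ≥ 5 mm.
- As written: R = m.
- Baseline included: R = min(B, m).

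At the first on-treatment scan m = s, so as written s − R = 0 and target-growth PD is impossible.

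**Step 2: example courses.** The sums are hypothetical, in mm, with baseline first and then 8-weekly scans.

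| Sums | PD scan, baseline included | PD scan, as written | Check of the written rule |
|---|---|---|---|
| 100, 125, 150 | 1 | 2 | 150/125 = 1.20 |
| 100, 140, 165, 195 | 1 | 3 | 165/140 = 1.18; 195/140 = 1.39 |
| 100, then +20 per scan | 1 | 3 | 140/120 = 1.17; 160/120 = 1.33 |
| 100, then +10 per scan | 2 | 4 | 130/110 = 1.18; 140/110 = 1.27 |
| 100, then +10% per scan | 2 | 3 | 1.1² = 1.21 over the first scan |
| 100, 130, 132, 133, 135 | 1 | none in 4 scans | 135/130 = 1.04 |
| 100, 103, 125 | 2 | 2 | 125/103 = 1.21 |
| 100, 85, 90, 103, 120 | 3 | 3 | 103/85 = 1.21 |

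The pattern is:
- If growth from baseline reaches the threshold at the first on-treatment scan, a delay of at least one scan is certain.
- Under constant percentage growth the delay is one scan, since counting starts from scan 1 instead of baseline.
- If the threshold is first reached later and no sum has fallen below baseline, the date may be late, or unchanged when the first on-treatment sum is close to baseline (100, 103, 125).
- If an earlier on-treatment sum is below baseline, then min(B, m) = m and the two rules agree.

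**Step 3: how many patients could be affected at the first scan.** One scan interval is 56/30.4375 = 1.84 months. The only TTP medians in the plan are those in Section 1.2 for first-line sorafenib, 4.2 and 3.8 months. They are used here as an assumption, with exponential times. The share progressing by week 8 is 1 − 2^(−1.84/median):
- median 3.8 months: 0.285, and 0.285 × 32 = 9.1 patients;
- median 4.2 months: 0.262, and 0.262 × 32 = 8.4 patients.

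These are progressions by any route. Under the assumption, they are an upper bound on those misdated at the first scan.

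**Step 4: effect on summaries.** Suppose progressions are read at 8-weekly scans and a share f of them is called one scan late. The documents do not give f.
- Mean time to documented PD rises by f × 1.84 months: 0.46 at f = 0.25, 0.92 at f = 0.5, 1.84 at f = 1.
- The progression-free share at week 8 becomes S(8) + f × [1 − S(8)]. For the 3.8-month median and f = 0.5 this is 0.715 + 0.5 × 0.285 = 0.857.
- The scan-read median is 3 × 1.84 = 5.5 months and stays there until S(24) + f × [S(16) − S(24)] reaches 0.5. For 3.8 months, S(16) = 0.511 and S(24) = 0.365, so f must reach (0.5 − 0.365)/(0.511 − 0.365) ≈ 0.92. For 4.2 months, S(16) = 0.545 and S(24) = 0.402, so f must reach (0.5 − 0.402)/(0.545 − 0.402) ≈ 0.69. Beyond that the median becomes 4 × 1.84 = 7.4 months.

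**The case against.** The best defence is that nobody would apply the rule literally. An increase measured against the same scan has no meaning, a baseline sum is recorded for every patient, RECIST v1.1 is the named standard, and the calendar assigns scan reading to a radiologist or an imaging core. Nothing in the documents shows that any site has used the literal reading. This stands as a limit on the claim: the harm is conditional on the text being applied as written. It does not cure the text. Section 7 writes out its own criteria, Section 5.5 points to them, and the plan does not say whether those criteria or the cited standard govern if they differ.

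A reader might infer a contradiction with Section 7.1.1, which says "Patients who exhibit objective disease progression prior to the end of cycle 1 will also be considered evaluable". That goes too far. Such progression can come from new lesions or non-target disease even under the literal rule. The sentence sits uneasily with the literal reading, but does not contradict it.

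A reader might also infer that no patient can be called PD at the first scan. New lesions, unequivocal non-target progression (which Table 6 accepts only exceptionally) and clinical progression leading to withdrawal all remain available, so this is not so. The patient who is missed is the one with target growth alone and no clinical progression that leads to withdrawal.

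**Conclusion.** The point holds as a defect of wording with a conditional effect. In all five places the stated progression reference omits the baseline sum, and the text gives nothing to put it back. Applied as written, it dates PD at least one scan (about 8 weeks) late in patients who reach the growth threshold at the first on-treatment scan by target lesions alone. It can also do so in patients who reach it later, provided no on-treatment sum has fallen below baseline.

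It would be tempting to conclude that median PFS and TTP are overstated by 8 weeks. The documents do not support that. The share of such patients is unknown, and on the assumed exponential times the scan-read median does not move when half of all progressions are called one scan late. Nor do they establish that patients stay on drug longer, because Section 5.5 lists other grounds for ending treatment.

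The consequences are confined to the descriptive PFS and TTP estimates and to SD versus PD. The primary endpoint is DLT, the 32 patients serve the dose-toxicity estimate, and no test rests on PFS or TTP. ORR is essentially unaffected because partial response is measured from baseline. It could change only for a patient whose lesions first grew past the PD threshold and later shrank by 30% from baseline.

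**What to change.** State the reference as the smallest sum recorded on study, including the baseline sum if that is the smallest, in all five places: Section 7.1.4.1 (PD and SD), Section 7.1.4.3, and Section 7.1.5 (both durations). In duration of response the change is for consistency only, since a responder's sum is already at least 30% below baseline.

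Say in Section 11.4 that PD dates for PFS and TTP are derived from the recorded target-lesion measurements under this definition, together with the other progression routes. Confirm which reference was used for patients already assessed, and re-derive their dates if it was the literal one.

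Section 5.5 relies on the Section 7 definition for ending treatment, so the sponsor must reconcile the two sections when the wording changes. This review takes no position on the treatment rule itself.

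The cost is one phrase in five places, one sentence in Section 11.4, and a re-derivation from measurements already held. No new scans or patients are needed.
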